8.2. Analyses of other continuous efficacy endpoints

Other continuous efficacy endpoints will be analyzed with ANCOVA models based on data with LOCF imputation and observed data as primary efficacy endpoints described above. The detailed statistical analyses are specified and marked as 'X' in Table 1.

Table 1: Statistical Analyses for Change and Percent Change Endpoints

		ANCOVA	
		LOCF	as Observed
Primary efficacy endpoint:			

 Percent change from baseline in weekly average WI-NRS score at Week 8 		X	X
other continuous efficacy endpoints: Change and percent change from baseline endpoints			
Related to pruritus:	- in weekly average of WI-NRS Pruritus over time	X	X
	-in Visual Analog Scale (VAS) over time	X	X
	- in 5-D Pruritus total score and subscales over time	X	X
	- in weekly itch severity score (a component of UAS7 (CIU only)) over time	X	X
Related to sleep	- in Sleep Loss VAS over time	X	X
	- in weekly average of difficulty falling asleep NRS over time	X	X
	- in weekly average of sleep quality NRS over time	X	X
Related to quality of life	- in DLQI total score over time	X	X
	- in ItchyQoL total score over time	X	X
	- in ItchyQoL symptom subscale score over time	X	X
	- in ItchyQoL functional subscale score over time	X	X
	-in ItchyQoL emotional subscale score over time	X	X

8.3. Responder Analysis

For primary efficacy endpoint and other selected efficacy endpoints, binary responder analyses will be conducted based on data with LOCF imputation or observed data described above.

Proportions of responders will be summarized, and 95% confidence intervals will be calculated based on binomial exact distribution. For statistical inference, odds ratios and corresponding 80% and 95% CIs will be calculated with Fisher exact tests.

Selected endpoints with responder analyses are listed in [Table 2](#).

Table 2: Statistical Analyses for Responders

	Fisher exact test	
Responder endpoints by visits	LOCF	As observed
Related to pruritus: • Weekly average WI-NRS with a ≥ 4 -point reduction	X	X
Related to sleep: • Difficulty falling asleep NRS with a ≥ 4 -point reduction • Sleep quality NRS with a ≥ 4 -point reduction	X X	X X
Related to quality of life: • DLQI total score with a ≥ 4 -point reduction	X	X
[REDACTED]	[REDACTED]	[REDACTED]

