**3.2 Secondary Efficacy Endpoints**

**Related to pruritus:**

- Change and percent change from baseline in weekly average of WI-NRS over time
- Change and percent change from baseline in Pruritus Visual Analog Scale (VAS) over time
- Change and percent change from baseline in 5-D Pruritus total score over time
- Proportion of subjects achieving at least a 4-point reduction from baseline in weekly average WI-NRS over time
- Change and percent change from baseline in weekly itch severity score, a component of Urticaria Activity Score 7 (UAS7) (CIU only)

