### **8.6.2 Key Secondary Endpoint Analyses**

For continuous secondary endpoints, the same ANCOVA models as primary endpoint will be used.

For categorical endpoints, frequency and percentage will be presented. Proportions of responders with 80% CI will be summarized and fisher exact tests will be conducted.

[REDACTED]

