3. DETERMINATION OF SAMPLE SIZE

This is a double-blind study. Each cohort will be independently analyzed. A total of approximately 26 subjects will be randomized in each cohort. The first 12 subjects will be randomized to the KPL-716 and the placebo arms in a 3:1 randomization ratio. The rest of the 14 subjects will be randomized in a 1:1 randomization ratio. There will be approximately 16 subjects and 10 subjects randomized to the KPL-716 arm and the placebo arm, respectively. Based on a two-sample t-test for the primary efficacy endpoint, change from baseline in weekly average of WI-NRS at Week 8, assumed mean changes of 4 for the KPL-716 arm and 1.5 for the placebo arm, a total sample size of 26 subjects per cohort will provide about 80% power to detect a 2.5-point mean difference with a standard deviation of 2.8, given a two-sided alpha of 0.2. Given the exploratory nature of this pilot study, the precision attained with the above cohort samples size is acceptable for early signal of efficacy assessments.

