5. GENERAL ASPECTS FOR STATISTICAL ANALYSIS

5.1. General Methods

- All analyses and summaries will be produced using SAS® version 9.4 (or higher).

- Descriptive statistics in each cohort will be presented for all endpoints and will include number of subjects (n), mean, standard error (SE) and standard deviation (SD), first quartile (Q1), median, third quartile (Q3), minimum and maximum for continuous variables. Where specified, 80% and 95% Confidence Intervals (CI) of the mean will be calculated.
- For categorical variables (including binary variables), counts and percentages will be presented. Where specified, 95% 2-sided CI for proportions and 80% and 95% for odds ratios will be presented. CI for proportions will be calculated based on exact binomial distribution.
- For inferential statistical analyses in each cohort, the efficacy data will be analyzed and displayed by treatment group (KPL-716 and placebo) and visits. Unless otherwise specified, all tests will be two-tailed using pre-specified levels of significance.
- Subject listings in all randomized subjects, except the listing for screen failures will be provided for all efficacy and safety data. In general, the subject listings will be sorted by treatment group, subject number and assessment date (and time, if applicable).
- In general, 1 year will be defined as 365.25 days and 1 month will be defined as 30.4375 days (365.25 days/12 months).

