17.9. Statistical Methods and SAS Codes

- **Analysis of Covariance (ANCOVA)**

The primary and secondary endpoints of change and percent change from baseline value by week will be analyzed using ANCOVA. The ANCOVA model includes factors of treatment, sex, and baseline value as a covariate. The following is an example of the SAS codes used to perform the analysis.

```
*****
```

* SAS Codes: *ANCOVA model*

* Variables in the model:

* chg = change from baseline in

* trt = treatment group code

* base = baseline value

* week = visit

```
*****;
```

```
proc mixed data=eff;  
  by week;  
  class trt;  
  model chg = trt base;  
  lsmeans trt /pdiff cl;  
run;
```

- **Fisher's Exact Test**

```
*****
```

* SAS Codes: Fisher's Exact Test

* Variables in the model:

* resp = response variable (Y/N or 1/0)

* trt = treatment group code

* week = visit number

```
*****;
```

```
proc freq data=dset order=data;  
  by week;
```

```
table trt*resp / alpha=0.05;  
exact relrisk fisher;  
output out=outname exact;  
run;
```

[REDACTED]

[REDACTED]

[REDACTED]

[REDACTED]

[REDACTED]

Signature Page for RIM-CLIN-001234 v1.0

Approval	[name] Legal 01-Oct-2021 12:48:07 GMT+0000
----------	---

Signature Page for RIM-CLIN-001234 v1.0

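### Responder effects between arms are planned only as ratios, which are infinite when no placebo subject responds; no readable passage plans a risk difference

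*SAP*

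**What the plan says.** The 4-point responder rate is a secondary endpoint (Protocol 3.2): "Proportion of subjects achieving at least a 4-point reduction from baseline in weekly average WI-NRS over time". The documents describe its analysis in four places:

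- **SAP 8.3.** Per arm: "Proportions of responders will be summarized, and 95% confidence intervals will be calculated based on binomial exact distribution". Between arms: "For statistical inference, odds ratios and corresponding 80% and 95% CIs will be calculated with Fisher exact tests". Table 2 applies this by visit to four readable endpoints (WI-NRS, two sleep scales, DLQI), with LOCF and as observed.
- **SAP 5.1.** The general rule for binary variables is the same: "95% 2-sided CI for proportions and 80% and 95% for odds ratios will be presented".
- **SAP 17.9.** The example code differs from the text. It asks for "exact relrisk fisher", which is a relative risk and Fisher's test, at the 95% level only ("table trt*resp / alpha=0.05").
- **Protocol 8.6.2.** "Proportions of responders with 80% CI will be summarized and fisher exact tests will be conducted". It names no between-arm effect measure.

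No readable passage plans a difference in proportions or says what to report when a cell is empty.

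**The concern.** Each cohort has about 10 placebo subjects, and the endpoint requires a large improvement. A table with no placebo responders is therefore an ordinary outcome. In such a table the odds ratio has a zero in its denominator, so the estimate and its upper limit are infinite. The relative risk of response has the same fault. If neither arm has a responder, both ratios are undefined.

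The loss is one of description. Cohorts with 4, 8 or 12 responders out of 16 on KPL-716 and none on placebo would all report the same point estimate and the same upper limit. The trial is meant to show which diseases respond, so the size of the responder effect is worth having. Choosing a substitute measure or a continuity correction after an empty cell has appeared would be a post hoc decision.

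**Working it through.** **Inputs.** From SAP 3: "assumed mean changes of 4 for the KPL-716 arm and 1.5 for the placebo arm", common SD 2.8, two-sided alpha 0.2, about 16 and 10 subjects. The arm sizes follow from the randomisation: 12 subjects at 3:1 give 9 and 3, then 14 at 1:1 give 7 and 7, so 16 and 10. The responder threshold is a reduction of 4 points. There are five cohorts, analysed separately.

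**Step 1. The plan's own figure.** The standard error is 2.8 × √(1/16 + 1/10) = 1.129 and the noncentrality is 2.5/1.129 = 2.215. With 24 degrees of freedom, the noncentral t gives power 0.815, which agrees with the stated 80% or so.

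**Step 2. Implied responder rates**, taking the changes as normal:

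- Placebo: 1 − Φ((4 − 1.5)/2.8) = 1 − Φ(0.893) = 0.186
- KPL-716: 1 − Φ((4 − 4)/2.8) = 0.500

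**Step 3. Chance of an empty placebo cell.**

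- Per cohort: (1 − 0.186)^10 = 0.128
- At least one of five independent cohorts: 1 − (1 − 0.128)^5 = 0.495
- Requiring at least one KPL-716 responder, so that the ratio is infinite and not 0/0, leaves 0.495, because 0.5^16 is about 0.00002.

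**Step 4. Sensitivity.**

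| Change from base case | Placebo rate | Per cohort | At least one of five |
|---|---|---|---|
| 8 evaluable on placebo | 0.186 | 0.193 | 0.66 |
| 9 evaluable | 0.186 | 0.157 | 0.57 |
| 11 evaluable | 0.186 | 0.104 | 0.42 |
| SD 2.5, 10 evaluable | 0.159 | 0.178 | 0.62 |
| SD 3.0, 10 evaluable | 0.202 | 0.104 | 0.42 |

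Fewer than 10 evaluable is plausible in the as-observed analysis, because SAP 8.1 sets assessments affected by rescue medication to missing. For other assumed placebo rates with 10 subjects, the per-cohort chance is 0.9^10 = 35% at a rate of 10%, and 0.75^10 = 5.6% at 25%.

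**Step 5. What each measure reports.** The score limits are the values d solving (p̂₁ − p̂₀ − d)/√V(d) = ±1.2816. Here V(d) uses the restricted maximum likelihood rates and the factor 26/25.

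| KPL-716 vs placebo | Odds ratio | Risk difference (80% score CI) |
|---|---|---|
| 4/16 vs 0/10 | infinite | 0.25 (0.09 to 0.41) |
| 8/16 vs 0/10 | infinite | 0.50 (0.33 to 0.66) |
| 12/16 vs 0/10 | infinite | 0.75 (0.58 to 0.86) |

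For 8/16 vs 0/10 the conditional exact interval for the odds ratio is 2.82 to infinity at 80% and 1.48 to infinity at 95%. Fisher's p is 0.009.

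**Step 6. Agreement of the score interval with Fisher's test.** I enumerated all 16-by-10 tables. The 80% score interval and Fisher's test at 0.2 disagree with probability 8.8% when the true rates are 50% and 18.6%, and 5.8% when both are 18.6%. An example is 8/16 vs 2/10. The score interval is 0.05 to 0.51, which excludes zero. Fisher's p is (579,150 + 114,400 + 8,008 + 454,961)/5,311,735 = 0.218.

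**The case against.** The strongest reply is that nothing essential is lost. A reader who sees 8/16 against 0/10 has both proportions with exact intervals and can subtract them. Fisher's test works normally: with no placebo responders and a 50% rate on KPL-716, it gives p below 0.2 with 99% probability. An interval open above is a valid result. All of this stands. It does not supply an interval for the difference, because two separate per-arm intervals do not give one.

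Second, the relative risk need not be infinite. The example code does not say which response column it analyses, and the relative risk of non-response in the same table is (8/16)/(10/10) = 0.50. That is correct, so the claim is limited to the relative risk of response. The code also shows that it would be too strong to call the odds ratio the only measure in the whole SAP; it is the only one in the text of 5.1 and 8.3.

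Third, an exact odds ratio is the natural partner of Fisher's test, and the score interval will sometimes disagree with that test. The cost is real (step 6). The planned pair does not always agree either. For 4/16 vs 0/10 the two-sided p is (1,820 + 210)/14,950 = 0.136, below 0.2. The one-sided tail is 1,820/14,950 = 0.122, above 0.10, so the equal-tailed 80% exact interval for the odds ratio still includes 1.

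Fourth, blacked-out blocks follow Protocol 8.6.2, the readable rows of Table 2 and the Fisher code. The statement that no risk difference is planned covers readable text only.

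**Conclusion.** The point holds as a gap in estimation for a secondary endpoint. When placebo has no responders, the planned odds ratio and the coded relative risk of response give no finite estimate and no upper limit, and nothing finite is planned beside them. The chance at Week 8 is about 13% per cohort. The figure of about 50% is for at least one of five cohorts and should not be read as the risk in any given cohort. Both rest on the plan's means and SD, normal changes on what is in fact a bounded scale, and 10 evaluable placebo subjects. The five-cohort figure also needs full enrolment and independence, whereas Protocol 4.1 and SAP 2.3 give 26 as a maximum.

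Three stronger readings are tempting, and the documents do not support them:

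- *A cohort with no placebo responders has no usable effect size.* Proportions, Fisher's p and a finite lower limit remain.
- *Cohorts cannot be compared on one scale.* The primary analysis (SAP 8.1) gives a least-squares mean difference with 80% and 95% intervals in each cohort.
- *The problem is worse at early weeks, or in a cohort stopped after about 12 subjects.* Neither document gives early placebo rates. The interim sections (Protocol 8.11, SAP 14) describe a look that informs the development plan and give no closure rule.

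**What to change.** In SAP 5.1 and 8.3, add the difference in responder proportions (KPL-716 minus placebo) with 80% and 95% Miettinen-Nurminen score intervals, for every Table 2 endpoint and visit, LOCF and as observed. In the 17.9 code:

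- request the risk difference with score limits at both confidence levels;
- request the odds ratio that the text promises;
- fix the row order and the response column explicitly, so that they do not depend on the order of the data.

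Keep Fisher's test and the exact odds ratio in every table, and report the odds ratio as infinite or not estimable when a cell is zero. Dropping it only from those tables would make the reporting depend on the data. State in advance that Fisher's p-value is the test and the risk difference is the estimate, so that the occasional disagreement (about 6% to 9% of tables in the two cases computed) needs no decision after the results are seen.

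The cost is a few sentences in the SAP and one more option in the existing procedure. No new data are needed, and the same edit removes the mismatch between text and code.

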## 4.6 Selection of Study Population

### 4.6.1 Inclusion Criteria

1. Male or female, aged 18 to 75 years, inclusive, at the time of consent.
2. Has a physician-documented diagnosis of the specified chronic pruritic disease. Duration of disease must be at least 6 months. The study dermatologist or the study allergist/immunologist confirms the diagnosis of the specified chronic pruritic disease. The duration of disease (at least 6 months) can be documented as affirmed by the subject.
  - Pruritus associated with these diagnoses must be refractory to treatment with H1 antihistamines and must have been present for at least 6 weeks prior to Day 1
  - Subjects with CIU must have had pruritus and hives for at least 6 consecutive weeks prior to Day 1. In subjects with CIU, urticarial eruptions must typically last less than 24 hours
3. Has moderate to severe pruritus, defined as WI-NRS  $\geq 7$  at the Screening Visit and a mean weekly WI-NRS  $\geq 5$  for each of the two consecutive weeks immediately prior to randomization.
4. Sexually active female subjects must be:
  - postmenopausal, defined as at least 12 consecutive months post cessation of menses (without an alternative medical cause) and confirmed by a follicular stimulating hormone (FSH) test, or
  - surgically sterile following documented hysterectomy, bilateral salpingectomy, bilateral oophorectomy or
  - nonpregnant, nonlactating, and having agreed to use a highly effective method of contraception from the Screening Visit until 16 weeks after final study drug administration
    - Note: highly effective methods of contraception include:
      - hormonal contraceptives associated with inhibition of ovulation (stable dose for at least 4 weeks prior to first dose)
      - intrauterine device (IUD)
      - intrauterine system (IUS)
      - double barrier methods of contraception (barrier methods include male condom, female condom, cervical cap, diaphragm, contraceptive sponge) in conjunction with spermicide
      - tubal ligation
      - vasectomized male partner

5. Sexually active male subjects must have documented vasectomy or must agree to use a highly effective method of contraception as defined above with their partners of childbearing potential from first dose until 16 weeks after final study drug administration.

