- **WI-NRS score:** Subjects will be asked daily to assign a numerical score to the intensity of their most severe (worst) pruritus in the past 24 hours using a scale from 0 to 10, with 0 indicating no pruritus and 10 indicating the worst imaginable pruritus. The Worst-Itch NRS is provided in the Daily NRS Tool Section 17.2.

- The sleep quality NRS: Subjects will be asked daily to assign a numerical score to the quality of their sleep in the previous night using a scale from 0 to 10, with 0 indicating best possible sleep and 10 indicating worst possible sleep. The sleep quality NRS is provided in the Daily NRS Tool (Section 17.2).
- The difficulty falling asleep NRS: Subjects will be asked daily to assign a numerical score to the intensity of their difficulty falling asleep last night due to itch using a scale from 0 to 10, with 0 indicating not difficult at all and 10 indicating extremely difficult. The difficulty falling asleep NRS is provided in the Daily NRS Tool (Section 17.2).
- Pruritus VAS: Subjects will be asked to place a line perpendicular to the VAS line at the point that represents the intensity of their average pruritus experienced over the previous three days using a scale from 0 to 10, with 0 indicating no pruritus and 10 indicating the worst imaginable pruritus. Pruritus VAS scale is provided in Section 17.3.
- Sleep Loss VAS: Subjects will be asked to place a line perpendicular to the VAS line at the point that represents the intensity of their average sleeplessness experienced over the previous 3 nights using a scale from 0 to 10, with 0 indicating no sleeplessness and 10 indicating the worst imaginable sleeplessness at every visit. The scale of Sleep Loss VAS can be found in Section 17.3.
- The 5-D Pruritus Scale: This tool evaluates pruritus in five domains: duration, degree, direction, disability and distribution. Duration, degree and direction each consist of one item. The disability domain contains four items and the distribution domain includes 16 items. The first four domains are measured on a five-point Likert scale. The scores from each domain are added together to obtain a total 5-D score ranging from 5 (no pruritus) and 25 (most severe pruritus) (Elman 2010). The 5-D Pruritus Scale is administered every two (2) visits. The score of each of the 5 domains is obtained separately and summed together to get the total 5D-pruritus score.
 - For duration, degree and direction, use the number indicated below the response choice.

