4.2. Modified Intent-to-Treat (mITT) Analysis Set

All randomized subjects who receive at least one (1) dose of KPL-716 or placebo and have at least one (1) post-baseline efficacy assessment in the double-blind Treatment Period will be included in the modified intent-to-treat (mITT) analysis set. All mITT analyses will be based on each subject's randomized treatment assignment.

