8. EFFICACY ANALYSES

All efficacy analyses will be performed in the mITT analysis set. The analysis of primary efficacy endpoint will be repeated in the PP population. Analysis based on the mITT set will be the primary analysis and the analyses based on other analysis sets will be considered as the supportive analyses.

Line plots of LS Mean (SE) in percent change from baseline based on ANCOVA overtime will be presented and bar charts for responder analysis will be provided as well if needed for selected endpoints.

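### The 4-point responder analyses of sleep and DLQI count subjects who start below 4 as certain non-responders, and percent change on these scales breaks down at or near a zero baseline

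*SAP*

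**What the plan says.** **Responder rule.** SAP section 8.3, Table 2 defines response as a fall of 4 points or more. Besides weekly average WI-NRS, the readable rows are "Difficulty falling asleep NRS with a", "Sleep quality NRS with a" and "DLQI total score with a", each followed by that threshold. None carries a condition on the baseline score. One further row is redacted and is not considered here. Inference is by Fisher's exact test with odds ratios.

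**Denominator.** SAP section 8 states: "All efficacy analyses will be performed in the mITT analysis set". Section 4.2 admits randomized and dosed subjects who "have at least one (1) post-baseline efficacy assessment in the double-blind Treatment Period will be included in the modified intent-to-treat (mITT) analysis set". Baseline score plays no part.

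**Entry criteria.** Protocol section 4.6.1, criterion 3 reads "Has moderate to severe pruritus, defined as WI-NRS" of at least 7 at screening, plus a weekly mean of at least 5 in each of the two weeks before randomization. No criterion sets a minimum on either sleep NRS, Sleep Loss VAS or DLQI.

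**Scales.** SAP section 2.3 describes sleep quality as scored "using a scale from 0 to 10, with 0 indicating best possible sleep and 10 indicating worst possible sleep". Difficulty falling asleep and Sleep Loss VAS also run from 0 to 10, and DLQI from 0 to 30. For daily scores, baseline is a 7-day mean (SAP section 5.2).

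**Percent change.** SAP section 8.2, Table 1 applies ANCOVA, with LOCF and as observed, to "other continuous efficacy endpoints: Change and percent change from baseline endpoints". The rows include Sleep Loss VAS, both sleep NRS scores and DLQI. No rule is given for a zero or near-zero baseline.

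**The concern.** The 4-point rule suits WI-NRS, where entry guarantees room to fall by 4. The SAP carries it over to scales without that guarantee. On those scales a non-response can mean either that a subject had sleep or quality-of-life impairment that did not improve, or that there was too little impairment to score. The table does not separate the two.

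Three consequences follow.

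- The risk difference and the odds ratio are pulled towards no effect by subjects who carry no information about response.
- Fisher's test has no baseline covariate. If the arms differ by chance in the share who start below 4, that difference enters the comparison directly. With about 10 placebo subjects per cohort, such an imbalance is plausible.
- Percent change divides by the baseline score. At 0 it does not exist, and near 0 a small movement becomes a very large percentage that can dominate the mean of a small arm. Section 8 of the SAP plans line plots of LS mean percent change for endpoints not yet named, so this could be visible in the report.

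**Working it through.** **1. The plan's own figure.** SAP section 3 gives 16 v 10 subjects, a 2.5-point difference, SD 2.8, two-sided alpha 0.2 and about 80% power. Allocation: 12 × 0.75 + 14 × 0.5 = 16 and 12 × 0.25 + 14 × 0.5 = 10. The noncentral t with 24 degrees of freedom gives 81.5%, which agrees. This figure concerns the primary endpoint, which the present point does not touch. The arm sizes and alpha are used below.

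**2. Who cannot respond.** The largest possible fall from baseline b on a scale with minimum 0 is b. If b is below 4, a 4-point fall is impossible. If b is exactly 4, the score must reach 0. WI-NRS is exempt because its weekly mean at entry is at least 5.

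**3. Dilution.** Let f be the share with baseline below 4, equal in both arms, and let p1 and p2 be the response rates among those able to respond. The all-mITT rates are (1 − f)p1 and (1 − f)p2. The documents supply none of f, p1 or p2, so all three are assumptions. With p1 = 60% and p2 = 20%:

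| f | Rates, all mITT | Risk difference | Odds ratio |
|---|---|---|---|
| 0% | 60% v 20% | 40 points | 6.0 |
| 10% | 54% v 18% | 36 points | (0.54/0.46)/(0.18/0.82) = 5.3 |
| 20% | 48% v 16% | 32 points | (0.48/0.52)/(0.16/0.84) = 4.8 |
| 30% | 42% v 14% | 28 points | (0.42/0.58)/(0.14/0.86) = 4.4 |

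In numbers of subjects, 26f is 2.6, 5.2 or 7.8 per cohort. The risk ratio stays at 3.0 throughout, because equal shares cancel.

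**4. Power.** Exact enumeration of the two-sided Fisher test (p ≤ 0.2), with 16 v 10 in the full set. The restricted version thins each arm binomially to those with baseline of at least 4.

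| Response among those able | f | All mITT | Restricted |
|---|---|---|---|
| 60% v 20% | 10% | 62% | 66% |
| 60% v 20% | 20% | 57% | 65% |
| 60% v 20% | 30% | 53% | 58% |
| 50% v 15% | 30% | 50% | 49% |
| 50% v 15% | 40% | 43% | 40% |

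Restriction removes the dilution but also removes subjects, so power can rise or fall.

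**5. Chance imbalance.** Suppose there is no drug effect, with 40% response in both arms among those able to respond. If 20% of one arm and 40% of the other start below 4, the observed rates are 0.8 × 40% = 32% and 0.6 × 40% = 24%. That is an 8-point difference produced by baseline alone.

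**6. Percent change.** For a 1-point worsening, percent change is 100 × 1/b: undefined at 0, +700% at 1/7 (one day scored 1 in an otherwise zero week), +200% at 0.5, +100% at 1 and +20% at 5. In a placebo arm of 10 with nine subjects at −30%, one at +700% moves the mean from −30% to (9 × (−30) + 700)/10 = +43%. The 5-D total cannot be 0, because its minimum is 5, and the ItchyQoL bother items start at 1.

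**The case against.** The case against has real force on several points.

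- **The all-mITT proportion is legitimate.** Response among all treated subjects is a meaningful quantity, and the SAP may report it. This stands, and it is why the restricted table should be added and should not replace the planned one.
- **Loss of power.** A reader might infer that the trial loses appreciable power. The documents do not support that: the result depends on assumed rates, and in some scenarios restriction loses power.
- **Scale of the effect.** Inference in SAP section 8.3 is on the odds ratio, so a risk difference alone would be the wrong yardstick. The odds ratio is diluted too, though the risk ratio is not when the shares are equal.
- **Prevalence.** The share below 4 is unknown. Difficulty falling asleep is rated as due to itch, and itch has an entry floor. A DLQI below 4 may be uncommon in these subjects. Nothing in the criteria rules either out.
- **Percent change belongs to the protocol.** A reader might conclude that percent-change ANCOVA should survive only for WI-NRS. That goes too far. Protocol section 3.2 lists percent change for sleep and quality of life as secondary endpoints, section 8.6.2 gives continuous secondary endpoints the primary endpoint's ANCOVA, and the 5-D total has no zero-baseline problem.
- **Safeguards exist.** Absolute change with baseline as covariate is already planned for every one of these scales, and baseline scores are summarised. This limits the harm from percent change. It does nothing for the Fisher comparison.
- **Low stakes.** The only 4-point responder endpoint listed in protocol section 3.2 is WI-NRS. The sleep and DLQI versions are SAP additions in an exploratory pilot without multiplicity control. This stands.

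**Conclusion.** The point holds as a matter of interpretability. Under Table 2 as written, any mITT subject with a baseline below 4 on either sleep NRS or DLQI is a certain non-responder in either arm. The SAP does not say this in words; it follows from the mITT denominator and the absence of a baseline condition.

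If 10% to 30% start below 4, with true response of 60% v 20% among those able to respond, the reported risk difference is 36 to 28 points instead of 40, and the odds ratio about 5.3 to 4.4 instead of 6.0. These sizes rest on assumed shares and rates and on equal shares in the two arms. Unequal shares can distort the comparison in either direction. No power argument is made.

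Percent-change ANCOVA for Sleep Loss VAS, both sleep NRS scores and DLQI is undefined at baseline 0 and unstable near it. Without a written rule, a zero-baseline subject has no response value for the model to use.

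The point is minor. It concerns secondary and SAP-added analyses, and leaves the primary endpoint and its power as they are.

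**What to change.** Make both changes in the SAP before unblinding, because a baseline cut-off chosen afterwards would look data-driven.

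1. **Table 2.** For both sleep NRS scales and DLQI, add a pre-specified responder analysis restricted to subjects with a baseline of at least 4, showing n by arm. Keep the all-mITT version alongside it.
2. **Table 1.** For Sleep Loss VAS, both sleep NRS scales and DLQI, keep percent change as the protocol endpoint but summarise it descriptively (median, Q1, Q3), with a stated rule for zero baselines. Base inference on the absolute-change ANCOVA with baseline as covariate, which is already planned. Leave percent change for WI-NRS, the 5-D total and ItchyQoL as it is.

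The cost is SAP wording and one subset flag, with no new data. The restricted tables will have smaller denominators. Moving percent change on these scales from ANCOVA to a descriptive summary is a minor departure from protocol section 8.6.2, which the SAP should record with its reason.
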